##### **3.1.1 Safety or Full Analysis Set population (FAS)**

The Safety or Full Analysis Set population (FAS) will be defined as all participants who are randomized.

- In the event of subjects having received treatments that different from those assigned according to the randomized schedule, then the safety analyses will be conducted according to the treatment received rather than according to the randomization groups.
- Participants who are replaced and received at least one study medication will also be included in this population.

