#### 3.3.3.4.4 Terminal rate constant $\lambda z$

Terminal rate constant  $\lambda z$  is needed before we estimate  $AUC_{0-t}$ . Since we are expecting the terminal PK will have an exponential decline,  $\lambda z$  is estimated by:

- Find the PK after TMax
  - If there only 1 or 0 available PK readings after PK Tmax, then  $\lambda z$  will be set as missing.
- Do a regression of log-transformed PK vs Time
- $\lambda z$  is  $-1 * (\text{slope from this regression})$
- In a “No Peak” case,  $\lambda z$  will be set as missing

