#### 3.3.3.4.5 $AUC_{0-t}$

The  $AUC_{0-t}$  of PK over time will be calculated using trapezoid rule and the actual time points. Missing data for the calculation of the AUC will be handled as followed:

1. If the reading for Time 0 is missing, it will be the assumed as 0.
2. If any reading between Time 0 and Tmax is missing:
  - a. It will be imputed with linear interpolation.
3. If any reading after CMax is missing:
  - a. If  $\lambda z$  is available, it will be imputed using the regression line obtained when estimate  $\lambda z$
  - b. If  $\lambda z$  is missing,  $AUC_{0-t}$  will be set as missing.

We will calculate the following  $AUC_{0-t}$

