#### 3.3.3.4.6 $AUC_{0-\infty}$

$AUC_{0-\infty}$  is estimated as:

$AUC_{0-\infty} = AUC_{0-\text{last}} + AUC_{\text{last}}$ , where  $AUC_{\text{last}} = PK_{\text{last}}/\lambda z$ , and  $PK_{\text{last}}$  is the last available PK reading

- If  $\lambda z$  is missing, then  $AUC_{0-\infty}$  is set as missing.

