## **3.4.4 Efficacy Analysis**

All Efficacy analyses will be done for Safety/FAS population unless specified.

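### SAP 3.3.3.4.5 imputes post-Cmax PK readings with no limit beyond the last observed sample, so withdrawn participants get unflagged, partly extrapolated AUC(0-t) values that can exceed their own AUC(0-inf)

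*SAP*

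**What the plan says.** - **Imputation.** SAP 3.3.3.4.5 computes AUC(0-t) by the trapezoid rule on actual times. Its third missing-data rule begins "If any reading after CMax is missing". If λz is available, "it will be imputed using the regression line obtained when estimate" λz; if not, AUC(0-t) is set to missing. SAP Table 4 lists windows of 24 and 48 hours and 7, 14, 21 and 28 days.
- **λz.** SAP 3.3.3.4.4 instructs "Find the PK after TMax" and then "Do a regression of log-transformed PK vs Time". All post-Tmax readings enter, with no selection of a terminal phase. λz is missing "If there only 1 or 0 available PK readings after PK Tmax", so two readings are enough.
- **AUC(0-inf).** SAP 3.3.3.4.6 takes the area to the last reading and adds PK_last/λz, where PK_last "is the last available PK reading".
- **Default.** SAP 3.2.1 leaves missing data unestimated unless the plan specifies otherwise. Section 3.3.3.4.5 does specify otherwise.
- **Populations.** SAP 3.4.4: "All Efficacy analyses will be done for Safety/FAS population unless specified". SAP 3.4.4.1 repeats the PK analysis in PP. SAP 3.1.1: "Participants who are replaced and received at least one study medication will also be included in this population". PP (SAP 3.1.2) requires evaluable data only to Day 7.
- **Display.** SAP 3.3 puts original and calculated values in the listings. SAP 3.4.1 requires N in every continuous summary.

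AUC(0-28d) is named in the secondary PK objective of both documents.

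**The concern.** A rule that is reasonable for one missed sample between two observed ones also covers every sample lost after withdrawal. A participant last sampled at 72 hours would receive AUC(0-7d), (0-14d), (0-21d) and (0-28d), each resting on values read off a line fitted to the first three days. The dose-arm tables would show these beside fully observed values with nothing to tell them apart.

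The two exposure measures also treat the missing stretch differently. AUC(0-28d) follows the regression line and is integrated by trapezoid between visits. AUC(0-inf) stops at the last reading and adds an exponential tail. Nothing in the SAP makes them agree, so the area to Day 28 can come out larger than the area to infinity.

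Each cohort has three EXT608 participants, so one such value weighs heavily. Protocol sections 2 and 3.3.1 say these single-dose PK data are meant to guide the design of the patient study.

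**Working it through.** The documents state no AUC, half-life or dropout rate, so there is no figure to reproduce. The SAP rules were applied literally to assumed curves.

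**Assumptions (not in the documents).** PK samples at 0.25, 0.5, 1, 1.5, 2, 4, 8, 12, 18, 24, 48 and 72 h and at Days 5, 7, 14, 21 and 28; the public copy does not show the tables in protocol 7.1 and 7.1.1. First-order absorption with ka 0.3/h or 1/h. Linear trapezoid. PK_last read as the last observed value. No LLOQ, and no noise unless stated.

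**Step 1: one case in full.** Single-phase half-life 4 days, ka 0.3/h, last sample at 72 h.
- Observed: AUC(0-72h) = 54.04 and C(72h) = 0.6093. The fitted half-life is 96.96 h, so λz = 0.6931/96.96 = 0.00715/h.
- Values imputed at Days 5, 7, 14, 21 and 28: 0.4326, 0.3070, 0.0924, 0.0278, 0.0084.
- Trapezoids after 72 h: 48×(0.6093+0.4326)/2 = 25.0; 48×(0.4326+0.3070)/2 = 17.8; 168×(0.3070+0.0924)/2 = 33.5; 168×(0.0924+0.0278)/2 = 10.1; 168×(0.0278+0.0084)/2 = 3.0. Sum 89.4.
- AUC(0-28d) = 54.04 + 89.4 = 143.5, of which 89.4/143.5 = 62% is imputed.
- AUC(0-inf) = 54.04 + 0.6093/0.00715 = 139.3. Ratio 143.5/139.3 = 1.03.

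The excess comes from the linear trapezoid across 7-day gaps. It overstates exponential area by a factor 3.5k(1+e^(-7k))/(1-e^(-7k)), with k per day: 1.45 at a 2-day half-life, 1.12 at 4 days, 1.02 at 10 days.

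**Step 2: single-phase range (ka 0.3/h).** Imputed share of AUC(0-28d) by day of last sample, and AUC(0-28d)/AUC(0-inf) for a Day 3 leaver:

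| Half-life (days) | Day 3 | Day 5 | Day 7 | Day 14 | Ratio, Day 3 |
|---|---|---|---|---|---|
| 1 | 17% | 5% | 2% | 0% | 1.03 |
| 2 | 40% | 22% | 13% | 1% | 1.05 |
| 3 | 54% | 35% | 24% | 5% | 1.05 |
| 4 | 62% | 45% | 32% | 9% | 1.03 |
| 6 | 72% | 56% | 44% | 17% | 0.98 |
| 10 | 79% | 67% | 56% | 28% | 0.86 |

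In these curves the imputed AUC(0-28d) matches the full-sample value to within about 1%. With 20% lognormal noise and a Day 3 leaver, the chance that AUC(0-28d) exceeds AUC(0-inf) is 0.92 at 2 days, 0.59 at 4 days and 0.40 at 10 days, among fits with λz above zero.

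**Step 3: two-phase decline, last sample at 72 h, ka 1/h.** Both AUCs are divided by the full-sample AUC(0-28d):

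| Early/late half-life (h), slow fraction | AUC(0-28d) | AUC(0-inf) | Imputed share |
|---|---|---|---|
| 8/72, 0.3 | 0.77 | 0.75 | 25% |
| 8/120, 0.3 | 0.63 | 0.61 | 33% |
| 12/168, 0.3 | 0.55 | 0.53 | 33% |
| 8/72, 0.1 | 0.80 | 0.79 | 10% |

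Fitted half-lives are 18-40 h against true late half-lives of 72-168 h. AUC(0-inf) is as low as AUC(0-28d), so the shortfall comes from fitting λz to all post-Tmax points. For the same curves with last sample on Day 14, the AUC(0-28d) ratio is 0.95-0.995 and 2-13% is imputed. A more extreme curve (24/240 h, slow fraction 0.5) gives 97.5/167.0 = 0.58 with 52% imputed.

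**Step 4: weight in the arm.** A leaver without Day 7 data is replaced (protocol 4.4) but stays in the FAS, so is 1 of 4 values. A later leaver is normally 1 of 3, in both FAS and PP. If four participants had equal true exposure, a ratio of 0.80 gives an arm mean of (3+0.80)/4 = 0.95, and 0.55 gives (3+0.55)/4 = 0.89.

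**The case against.** A reader might infer that a withdrawn participant's AUC(0-28d) is generally mostly invented and also biased. The documents do not support that. They give no half-life, and the imputed share runs from about 0% to 79% in the single-phase table. In the four two-phase curves, where the level is clearly wrong, it is only 10-33%. Where it is well above half, decline is single-phase and the level is right. The one curve that is both low and mostly imputed reaches 52%. SAP 3.3.3.4.4 itself expects exponential decline.

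A reader might also infer that AUC(0-28d) always exceeds AUC(0-inf). It does not: the noise-free single-phase ratio falls below 1 between half-lives of 4 and 6 days. The excess also depends on two readings of the text. If the last available reading may be an imputed one, AUC(0-inf) in Step 1 becomes 144.6 against 143.5 and the excess disappears. If the regression line were integrated exactly, the ratio in the four two-phase cases would be 0.96-0.98.

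Several safeguards exist. AUC(0-t) is missing when λz is missing. The listings show substituted values, and N is already required. PP excludes anyone without evaluable Day 7 data. The early-termination visit (protocol 7.2.8) may add one real sample. Setting AUC(0-t) to missing is partly a matter of preference and can leave two values in an arm.

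All of this stands and limits the size of the point. None of it supplies a limit on the rule, a flag in the summary tables, or agreement between the two tails.

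**Conclusion.** The point holds in a limited form. As written, the SAP extrapolates a withdrawn participant's curve to Day 28 and summarises the result as an ordinary AUC(0-t). The values are partly extrapolated. They become mostly so only for an early leaver with a long enough half-life: about 3 days or more when the last sample is on Day 3, between 4 and 6 days for Day 5, about 8 days for Day 7.

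AUC(0-28d) can exceed the same person's AUC(0-inf), by about 1-5% in the noise-free cases and not at single-phase half-lives of about 6 days or more. Assay noise can produce it there too. This is an incoherence between two reported quantities, not a large error in exposure.

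The larger shortfall, 0.55-0.80 of the full-sample value for a Day 3 leaver, arises only if decline is two-phase. It belongs mainly to the λz fit and affects AUC(0-inf) equally. With single-phase decline the level is right.

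All figures rest on the assumed sampling times and half-lives. The change is worth making because the endpoint is a named secondary one with three active participants per dose, and the cost is only wording.

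**What to change.** Amend the SAP as follows.

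1. In 3.3.3.4.5, limit rule 3a to a missing sample lying between two observed post-Cmax samples.
2. For t beyond the participant's last observed sample, set AUC(0-t) to missing in the summaries.
3. Give any extrapolated AUC(0-t) in the listing only, flagged with its extrapolated percentage and computed with the same tail as AUC(0-inf): AUC(0-last) + (C_last/λz)(1 - exp(-λz(t - t_last))). In Step 1 this gives 138.1 against an AUC(0-inf) of 139.3, and with λz above zero it cannot exceed AUC(0-inf).
4. In 3.3.3.4.6, state that the last available PK reading is the last observed one.

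The formula needs λz above zero, and the SAP has no rule for a zero or negative slope. With 20% noise and a Day 3 leaver, such a slope arose in about 13% of fits at a 4-day half-life and 34% at 10 days, so the listing rule should say what is then shown.

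The cost is SAP wording, with no change to conduct. Fewer participants will contribute to the later AUC(0-t) summaries, which the N already required by SAP 3.4.1 will show. The fix leaves the all-points λz fit as it is, and with it half-life, AUC(0-inf), CL/F and Vz/F.

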**Table 4  $AUC_{0-t}$**

AUC 0-24 Hour
AUC 0-48 Hour
AUC 0-7 Day
AUC 0-14 Day
AUC 0-21 Day
AUC 0-28 Day

#### 3.3.3.4.6 $AUC_{0-\infty}$

$AUC_{0-\infty}$  is estimated as:

$AUC_{0-\infty} = AUC_{0-\text{last}} + AUC_{\text{last}}$ , where  $AUC_{\text{last}} = PK_{\text{last}}/\lambda z$ , and  $PK_{\text{last}}$  is the last available PK reading

- If  $\lambda z$  is missing, then  $AUC_{0-\infty}$  is set as missing.

## EXTBIO EXT608-101 Statistical Analysis Plan, V2, 2023-JULY-04

**3.3.3.4.7 Time to Half-Maximal PK, Both Early and Late ( $t_{Half,early}$  &  $t_{Half,late}$ )**

$T_{half,early}$  is the time in minutes, from time 0, to the time when PK rises to half way to the maximum. It is calculated as followed:

- $T_{half,early} = \text{Time corresponding to } \frac{C_{Max}}{2} \text{. } t_0$ , linear interpolation may be used if needed.
- If  $C_{Max}$  is missing,  $T_{half,early}$  will also be set as missing.

$T_{half,late}$  is the # of days, from  $T_{Max}$ , to the time when PK reduced to half way to the maximum.

Since we assume the PK is exponential decline,  $T_{half,late}$  is calculated as followed

- $T_{half,late} = \frac{\ln(2)}{\lambda z}$
- If  $\lambda z$  is missing,  $T_{half,late}$  will also be set as missing.

**3.3.3.4.8 Clearance (CL/F)**

Clearance is calculated as the dose divided by the  $AUC_{0-\infty}$  :

- $CL/F = \frac{Dose}{AUC_{0-\infty}}$
- If is missing, then CL/F is set as missing.

**3.3.3.4.9 Volume Distribution (Vz/F)**

Volume Distribution is calculated as:

- $Vz/F = \frac{Dose}{\lambda z * AUC_{0-\infty}}$
- If  $\lambda z$  is missing, then Vz/F is set as missing.

**3.3.3.5 PD Parameters**

The PD variables include:

- Serum total calcium (corrected for albumin)(Se-Ca)
- Phosphate
- Magnesium
- Creatinine
- Serum PTH
- Creatinine with estimated GFR
- 25-hydroxy-vitamin D (25-OH-D)
- 1,25-dihydroxy-vitamin D (1,25-OH-D)

**3.3.3.5.1 Change from baseline**

Change from baseline will be calculated for all numeric variables where baseline is the measurement at Day -1.

- Baseline will be the measurements collected on Day 0 Pre-Dose.

## EXTBIO EXT608-101 Statistical Analysis Plan, V2, 2023-JULY-04

- If the measurements on Day 0 Pre-dose is not available, the measurements collected on day -1 will be used.

**3.3.3.5.2 Change of severity status along time**

Additionally, the change of severity (normal/abnormal) status along time will also be categorized. The severity is determined by lab and reported to IMD directly.

In the EDC, the abnormal status is defined as:

- L = Low
- H = High
- A = Abnormal
- If the abnormal status variable is blank, then it is considered as Normal.

The change between two consecutive time points will be categorized based on the reported severity starting from baseline. The following category will be evaluated:

- Normal -> Normal
- Normal -> High
- Normal -> Low
- Normal -> Abnormal
- High -> High
- High -> Normal
- High -> Low
- Low -> Low
- Low -> Normal
- Low -> High
- Abnormal -> Abnormal
- Abnormal -> Normal
- Unknown (if lab test results at any of the consecutive time points is missing)

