##### 3.1.4 Dose Limiting Toxicity (DLT) Criteria

A potential DLT is defined as any of the following EXT608 TEAEs that occurs during the DLT period, graded according to the NCI Common Terminology Criteria for Adverse Events (CTCAE), Version 5.0 (2):

- Grade = 3 TEAE
- Grade = 3 anemia
- Grade = 3 AST/ALT elevation; and/or
- Grade = 2 AST/ALT elevation and Grade = 2 Bilirubin elevation

- Grade = 3 QTc prolongation
- Grade = 3 Hyper- and/or Hypotension
- Grade = 2 Hyperparathyroidism
- Grade = 2 Hyperthyroidism
- Grade = 3 Hypercalcemia
- Grade = 3 Hypocalcemia
- Grade = 3 Hypophosphatemia
- Grade = 3 Hypomagnesemia
- Grade = 3 Creatinine increased

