## 1.2 OBJECTIVES

### 1.2.1 Primary Objective

The primary objective is to characterize the safety and tolerability profile of escalating dose levels of EXT608 when administered to healthy adult participants as a single injection as assessed by:

- Incidence, nature, and severity of adverse events (AEs) and withdrawals due to treatment emergent AEs (TEAEs) [Time Frame: Day 0 up to Day 28]
- Frequency and severity of post-dose change from baseline in hematology, serum chemistries, urinalysis, electrocardiogram (ECG), vital signs, and physical examination (Exam) findings [Time Frame: Day 0 up to Day 28]
- Percentage of participants with injection or infusion site reactions [Time Frame: Day 0 to Day 7]

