#### **3.4.5.2 Laboratory tests Results**

This section will describe the summary of safety lab test results. Summary of PK and PD results are described in previous section (3.4.4.1 and 3.4.4.2).

All safety lab test results will be listed. Additionally, each Lab Test results of each subject at different time points will be plot against the time points to show the trend.

The change of baseline of any numeric safety lab results will be for each treatment arm.

The change of severity (normal/abnormal) status of each safety lab results along time will also be summarized for each treatment arm.

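### The SAP calls the laboratory's reference-range flag 'severity', so the only categorical severity summary of laboratory results carries no magnitude and no CTCAE grade is planned in the SAP text

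*SAP*

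**What the plan says.** The second primary measure in SAP 1.2.1, which matches Protocol 2.1, is "Frequency and severity of post-dose change from baseline in hematology, serum chemistries, urinalysis, electrocardiogram (ECG), vital signs, and physical examination (Exam) findings", from Day 0 to Day 28.

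For laboratory data, SAP 3.3.3.5.2 sets up the severity variable: "Additionally, the change of severity (normal/abnormal) status along time will also be categorized". Its source is the laboratory: "The severity is determined by lab and reported to IMD directly". The recorded values are L, H and A, and for the remaining case "If the abnormal status variable is blank, then it is considered as Normal". Shifts are then formed visit to visit: "The change between two consecutive time points will be categorized based on the reported severity starting from baseline".

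That section is written for PD variables. SAP 3.3.4.4 applies the same handling to safety laboratory variables, and SAP 3.4.5.2 makes it a planned output: "The change of severity (normal/abnormal) status of each safety lab results along time will also be summarized for each treatment arm".

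The protocol uses a graded scale elsewhere. Potential DLTs in Protocol 3.1.4 are "graded according to the NCI Common Terminology Criteria for Adverse Events (CTCAE), Version 5.0", and Protocol 3.1.5 bases escalation on CTCAE v5.0 and serum calcium. Protocol 8.3 promises shift tables for laboratory change from baseline and does not say whether they are by grade or by range status.

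**The concern.** Severity in a primary safety measure should say how bad an abnormality was. A reference-range flag says only that a value left the range and, for L and H, in which direction. Once a participant is flagged High, further worsening does not show in the table, and the visit-to-visit category reads as no change.

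At stake is how the final report answers the severity part of the second primary measure for laboratory results. The protocol has already named the scale on which it judges laboratory toxicity. If the report summarises severity on a different scale without magnitude, a reader cannot see from any table described in the SAP text how many participants at each dose reached a given laboratory grade.

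**Working it through.** No alpha, power, effect size or sample-size formula enters this point, and the plan states no figure to reproduce. The check is a trace through the documents, two counts and one illustration.

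**1. Is there any other laboratory severity variable in the SAP?** The SAP text never mentions CTCAE. Its only grade is the 1 to 4 erythema grade in 3.3.4.5. SAP 3.3 says it covers any calculation applied to a variable before analysis, and a laboratory grade is such a calculation, but none is given.

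**2. Do the adverse event tables supply the grade?** Protocol 6.10.1.1 allows an abnormal laboratory finding to be an AE, and SAP 3.4.5.1 counts TEAEs by preferred term and intensity. Intensity is mild, moderate or severe, defined by interference with daily activities. A symptomless laboratory change can be rated mild whatever its size, and it is counted only if reported as an AE. So these tables do not supply a CTCAE grade.

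**3. How much of the DLT list is laboratory-based?** Protocol 3.1.4 has 13 items.
- Named laboratory abnormalities: anemia; AST/ALT; AST/ALT together with bilirubin; hypercalcemia; hypocalcemia; hypophosphatemia; hypomagnesemia; creatinine increased. That is 8.
- Others: any Grade 3 TEAE; QTc; hyper- or hypotension; hyperparathyroidism; hyperthyroidism. That is 5, and 8 + 5 = 13.

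Each of the 8 is set at a grade (2 or 3). The flag has no grades, so it cannot identify any of them.

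**4. What does the flag do to serum calcium?** Rule 5 in Protocol 3.1.5 uses an average peak more than 1.5 mg/dL above ULN. The 0.1 and 1.6 mg/dL values below are illustrative; only 1.5 comes from the documents. Each cohort has 3 active participants.

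| | Cohort X | Cohort Y |
|---|---|---|
| Peak above ULN, each participant (mg/dL) | 0.1, 0.1, 0.1 | 1.6, 1.6, 1.6 |
| Mean peak above ULN | (3 × 0.1)/3 = 0.1 | (3 × 1.6)/3 = 1.6 |
| Above the 1.5 limit? | No | Yes |
| Flagged High | 3/3 | 3/3 |

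The two cohorts can give identical transition tables. One participant who goes from 0.1 to 1.6 mg/dL above ULN between visits is recorded as High to High.

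**5. Are the flag categories complete?** Four states allow 4 × 4 = 16 transitions. The SAP lists 12, plus Unknown. High to Abnormal, Low to Abnormal, Abnormal to High and Abnormal to Low have no category. This is a minor side point, but it can be corrected in the same edit.

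**The case against.** The strongest reply is that magnitude is analysed elsewhere. Change from baseline is calculated for all numeric variables (SAP 3.3.3.5.1, extended to safety laboratory results by 3.3.4.4), and the default continuous summary includes minimum and maximum (3.4.1). All safety laboratory results are listed and plotted by subject (3.4.5.2). Serum calcium, phosphate, magnesium and creatinine are also PD variables, summarised by arm as values and as change (3.3.3.5, 3.4.4.2). With three active participants per cohort, the listings are readable line by line. This stands. A reader might infer that the plan cannot tell a trivial excursion from a large one. The documents do not support that; only the categorical severity summary has this limit. What the numeric outputs lack is a count of participants by grade. Change from baseline does not place a value against ULN or a grade, and summaries of single tests cannot show the AST/ALT-with-bilirubin item, which needs two results in the same participant.

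A second reply is that Protocol 8.3 promises only shift tables, so a range-status shift fits its wording. That is also correct, and the SAP does not contradict 8.3 on this. But a flag shift does not answer the word severity in the primary measure.

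A reader might also infer that escalation decisions are impaired. The documents do not support this either. Rule 5 acts on calcium in mg/dL, potential DLTs go to the DMB under the Safety Plan (Protocol 4.3.1.3), and interim summaries are left to the safety monitoring plan (SAP 3.5). Nothing ties the flag to those decisions.

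Nor can it be said that the final report will hold no count at DLT grade. The planned table list is an attached file (SAP section 4) and the Safety Plan is a separate document; neither is available here. The supportable statement is that the SAP text describes no such count.

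**Conclusion.** The point holds as a fault of labelling and of a missing summary. The SAP names reference-range status as severity, and the only categorical severity summary for the laboratory part of the second primary measure therefore has no magnitude. No analysis described in the SAP text counts participants by laboratory grade, although 8 of the 13 potential-DLT items in Protocol 3.1.4 are named laboratory abnormalities defined at a grade.

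The consequence is limited to final reporting. No data are lost, no estimate is biased, and magnitude can be recovered from the listings, plots and numeric summaries. The change is worth making because the measure is primary and the protocol has already chosen the scale.

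The conclusion assumes that the unseen table list adds no graded laboratory table. CTCAE cut-offs are not in the documents, so no grade boundary was computed here, and how many of the 8 items can be graded from a value alone is not established.

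**What to change.** In SAP 3.3.3.5.2, 3.3.4.4 and 3.4.5.2:

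- Rename the L/H/A/blank variable reference-range status and stop calling it severity. Add the four missing transitions, or state why they cannot occur.
- For each laboratory test with a numeric CTCAE v5.0 criterion, derive the grade at baseline and at each post-dose time point.
- Tabulate by arm, with placebo pooled, each participant's worst post-dose grade against baseline grade.
- List every result that meets a laboratory item in Protocol 3.1.4, with AST/ALT and bilirubin considered together within a participant.
- Keep the flag table for tests that have no numeric criterion.

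If the attached table list already contains a graded laboratory table, the SAP text needs only the derivation and a reference to that table.

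The cost is some programming and a few extra tables, using results the study already plans to collect. Before programming, each test must be checked against CTCAE v5.0 to see whether the value alone is enough to assign a grade.

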### **Statistical Analyses**

AEs will be presented in listings and TEAEs will be summarized. Individual results of laboratory tests (hematology, chemistry, and urinalysis) will be listed and change from baseline will be summarized using shift tables. Individual results of vital signs will be listed and observed values and changes from baseline will be summarized.

Individual results of quantitative ECG parameters from the 12-lead safety ECGs will be listed and observed values and changes from baseline will be summarized and analyzed consistent with the ICH E14 (3).

All summaries will be performed by placebo and each EXT608 dose level. Placebo data will be pooled across cohorts. Physical exam findings will be presented in data listings.

Concentrations of EXT608 will be summarized by dose over each scheduled sampling time using descriptive statistics. Individual plasma concentration data versus time will be presented in a data listing. PK parameters will be summarized by dose using descriptive statistics. Dose proportionality will be assessed graphically and using a power model. PD will be presented in listings and summarized by dose and time point.

Detection of ADA and NAbs will be presented in listings and summarized by dose and time point.

No formal hypothesis testing will be conducted as part of this study.

DMB data packages will be based on the FAS for safety and PP for PK/PD.

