### 8.3 Data Analysis

AEs will be presented in listings and Treatment Emergent Adverse Events (TEAEs) will be summarized. Individual results of laboratory tests (hematology, chemistry, and urinalysis) will be listed and change from baseline will be summarized using shift tables. Individual results of vital signs will be listed and observed values and changes from baseline will be summarized.

Individual results of quantitative ECG parameters from the 12-lead safety ECGs will be listed and observed values and changes from baseline will be summarized and analyzed consistent with the ICH E14 (3).

All summaries will be performed by placebo and each EXT608 dose level. Placebo data will be pooled across cohorts. Physical exam findings will be presented in data listings.

Concentrations of EXT608 will be summarized by dose over each scheduled sampling time using descriptive statistics. Individual plasma concentration data versus time will be presented in a data listing. PK parameters will be summarized by dose using descriptive

statistics. Dose proportionality will be assessed graphically and using a power model. PD will be presented in listings and summarized by dose and time point.

Detection of ADA and NAbs will be presented in listings and summarized by dose and time point.

No formal hypothesis testing will be conducted as part of this study.

DMB data packages will be based on the FAS for safety and PP for PK/PD.

Further details are described in the Statistical Analysis Plan.

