**1.4 MODIFICATIONS FROM THE STATISTICAL SECTION IN THE PROTOCOL**

None

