#### 3.3.4.4 *Lab evaluations*

Handling of the safety lab variables will be the same as the PD variables (section 3.3.3.5)

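### The SAP's only categorical lab summary compares each time point with the one before, whereas the protocol specifies shift tables from baseline, and SAP 1.4 declares no departure (minor)

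*SAP*

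**What the plan says.** Protocol 8.3 (Data Analysis) states that for laboratory tests "change from baseline will be summarized using shift tables". The synopsis, under Statistical Analyses, says the same.

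SAP 3.3.3.5.2 defines the categorical summary: "The change between two consecutive time points will be categorized based on the reported severity starting from baseline". Its missing-data category is "Unknown (if lab test results at any of the consecutive time points is missing". SAP 3.3.4.4 carries the rule to the safety labs: "Handling of the safety lab variables will be the same as the PD variables (section 3.3.3.5". SAP 3.4.5.2 then provides that the change of normal/abnormal "status of each safety lab results along time will also be summarized for each treatment arm". The same section keeps listings, a plot per subject and numeric change from baseline.

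SAP 1.4, headed "MODIFICATIONS FROM THE STATISTICAL SECTION IN THE PROTOCOL", contains the single entry None. The primary objective in SAP 1.2.1 includes "Frequency and severity of post-dose change from baseline in hematology, serum chemistries, urinalysis".

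SAP 3.3.3.5.1 gives two baselines for these variables: Day -1 in its opening sentence and Day 0 pre-dose in the bullet below it. The fallback that follows (Day -1 if the Day 0 pre-dose value is not available) fits the second.

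**The concern.** A shift table from baseline shows, for each participant, the status before dosing against the status after it. A chain of visit-to-visit changes answers a different question. After the first interval its reference is the previous visit, so a value that turns High and stays High appears once as Normal to High and then as High to High.

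Someone programming from the SAP would therefore produce a different table from the one the protocol specifies for a primary safety objective. A reader of SAP 1.4 would be told that nothing had changed. What is at stake is how clearly the main categorical lab table shows who became abnormal after dosing.

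**Working it through.** **1. The texts side by side.** The phrase on starting from baseline in SAP 3.3.3.5.2 fixes where the chain begins. It does not make baseline the reference for every visit, because the Unknown rule refers to consecutive time points and so only fits adjacent pairs. Where the SAP wants a status change from baseline it says so: physical exam status in SAP 3.3.1 runs from screening to Day 28 or end of study. No SAP section sets baseline lab status against a later status, except through the first interval.

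**2. A missed visit.** Assumption: the test is drawn at each of the five outpatient days in Protocol 3.1.6 (5, 7, 14, 21, 28), since the lab schedule is not readable.
- Example: Normal through Day 7, Day 14 missed and unfilled, High at Days 21 and 28. The last three consecutive entries are Unknown, Unknown, High to High. Against baseline, Day 14 is Unknown and Days 21 and 28 are both Normal to High.
- All cases: take one participant who is Normal before Day 5, with exactly one missed visit and the first High at the next visit. A miss at Day 5, 7, 14 or 21 leaves 3, 2, 1 or 0 later visits free, so the patterns number 8 + 4 + 2 + 1 = 15.
- The consecutive table shows no Normal to High if the free visits never go from Normal back to High. With m free visits that is m + 1 patterns: 4 + 3 + 2 + 1 = 10. In the other 5 a later recurrence supplies one. A baseline reference shows Normal to High in all 15.

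**3. A flagged baseline.** Protocol 4.2 criterion 20 excludes ALT or AST only above 1.5 times the ULN, so a baseline between the ULN and 1.5 times the ULN is possible. Write N for Normal and H for High at baseline, visit 1 and visit 2, for three participants:

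| Set | Sequences | Baseline to visit 1 | Visit 1 to visit 2 | Newly High |
|---|---|---|---|---|
| A | NNH, HNN, NNN | NN 2, HN 1 | NN 2, NH 1 | 1 of 3 |
| B | NNN, HNH, NNN | NN 2, HN 1 | NN 2, NH 1 | 0 of 3 |

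The consecutive tables are identical, although in set A one participant is newly High and in set B none is.

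**4. How general this is.** I enumerated every set of three participants with N/H status at baseline and three later visits, none missing. There are 2^4 = 16 sequences and C(18,3) = 816 sets, of which C(10,3) = 120 are all Normal at baseline. Tables are kept separate by interval or visit. A set is ambiguous if another set gives the same table but a different answer.

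| What is to be recovered | From | All 816 | All Normal at baseline (120) |
|---|---|---|---|
| By-visit baseline table | consecutive table | 416 | 0 |
| Number newly High | consecutive table | 148 | 16 |
| Number newly High | by-visit baseline table | 144 | 64 |
| Number newly High | both of these | 32 | 16 |
| Number newly High | baseline-to-worst table | 0 | 0 |

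The zeros in the last row hold by construction, because the number is a cell of that table. These are counts of patterns, not probabilities.

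**The case against.** The strongest reply is that little depends on this table. An arm has about three active participants. Every result is listed and plotted per subject, numeric change from baseline is summarized, and an abnormal lab finding can also be an adverse event (Protocol 6.10.1.1). This stands and limits the point to one summary.

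The missed-visit case is narrow. It needs an unfilled gap just before the first High, and SAP 3.2.3.1 and 3.2.3.2 allow some gaps to be filled. Of the 10 patterns, 7 have the miss at Day 5 or Day 7, and a participant without reliable Day 7 data is replaced (Protocol 4.4). Against that, a dosed participant who is replaced stays in the FAS (SAP 3.1.1), so those data are still tabulated.

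Complete urinalysis is scheduled at screening, Day -1 and end of study (Protocol 6.8.2.1). With one post-dose point the two tables coincide there, so the effect falls mainly on hematology and chemistry.

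Four stronger readings are tempting but not supported:
- *The protocol requires a by-visit baseline table.* Protocol 8.3 states no visit structure and no missing-data rule, and step 4 shows that a by-visit table is no better for counting the newly abnormal.
- *The hemoglobin criterion (Protocol 4.1, criterion 7) proves flagged baselines.* Its cut-offs are fixed in the protocol, whereas the flags in SAP 3.3.3.5.2 are set by the laboratory. Nothing shows that the two agree.
- *Dose escalation is affected.* Escalation rests on CTCAE grades and Se-Ca (Protocol 3.1.5), total Se-Ca must be within normal limits at entry, and SAP 3.5 leaves the interim outputs to a separate plan.
- *The final report will lack a baseline table.* SAP 4 refers to an attached list that is not available.

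**Conclusion.** The inconsistency holds and is minor. The protocol specifies shift tables from baseline, the SAP text defines a categorical lab summary between consecutive time points, and SAP 1.4 does not declare the difference.

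The consequence is limited to that summary. It arises when a visit is missed and unfilled just before a first abnormal value, or when a participant is flagged at baseline. With all baselines Normal and no missed visit, the consecutive table fully determines the by-visit baseline table.

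It would go too far to infer that the SAP abandons change from baseline for labs, since the numeric analysis keeps it. How often either situation will occur cannot be judged from the documents. The conclusion assumes that the laboratory flags values above its own ULN, that tables are kept separate by interval, and, for the missed-visit count, that the test is drawn at all five outpatient visits.

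**What to change.** 1. In SAP 3.3.3.5.2 and 3.4.5.2, define one baseline-referenced lab shift table by dose and pooled placebo: baseline status against worst post-dose status through Day 28, with High and Low separate. Use the analysis values already allowed by SAP 3.2.3.1 and 3.2.3.2. This table satisfies Protocol 8.3 and gives the number newly abnormal without ambiguity. A by-visit baseline table is optional.
2. Keep the consecutive table as supplementary.
3. Use a single baseline by reconciling the two statements in SAP 3.3.3.5.1. The existing fallback fits Day 0 pre-dose, with Day -1 as substitute.
4. If the sponsor prefers only the consecutive table, declare and explain the departure in SAP 1.4.

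Cost: SAP wording and one extra table to program. No new data and no protocol change are needed.
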